9.3.2.4. Shipping of Specimen(s)

Serum samples will be shipped frozen according to Section 9.3.1.4.

9.3.2.5. Site(s) Performing Correlative Study

ETCTN Central Laboratory: [name], The Analytical Pharmacology Core Laboratory at the Sidney Kimmel Comprehensive Cancer Center at Johns Hopkins (SKCCC)

9.4. Exploratory/Ancillary Correlative Studies

9.4.1. DNA and RNA sequencing of exploratory biomarkers

9.4.1.1. Collection of Specimen(s)

Bone marrow biopsy and aspiration will be performed at screening and at the end of study at the local study site. An optional bone marrow biopsy and aspiration will be performed pre-Cycle 2, Day 1. Immediately after marrow is aspirated, place 3-5 mL of bone marrow aspirate into sterile EDTA (lavender top) tube. Mix well by inversion. Bone marrow aspirate specimen should be labeled as per the Specimen Tracking Instructions (Section 9.1.1.1.). Buccal mucosa collection will also be performed at screening which will serve as a germline control for whole exome sequencing. See Appendix G for details regarding details of performing buccal swabs for the collection of buccal mucosa.

9.4.1.2. Handling and Processing of Specimens(s)

After bone marrow aspirate collection, specimen will be processed at the MD Anderson Tissue Qualification Laboratory (TQL) where it will be logged into the PowerPath database. Subsequently, the MD Anderson Molecular Diagnostics Laboratory (MDL) will perform CD138 bead enrichment from the bone marrow sample, followed by DNA and RNA extraction in a CLIA-certified environment. The MD Anderson MDL will also perform DNA extraction from the buccal mucosal swab which will serve as a germline control. The MD Anderson TQL and MDL will serve as a central site for myeloma tissue processing for the study.

For study sites outside of MD Anderson, bone marrow aspirates should be kept at room temperature until same-day overnight shipping at ambient temperature to the MD Anderson TQL where it will be logged prior to further processing. Buccal swab should be sent in the same specimen container as the bone marrow aspirate to the MD Anderson TQL.

The bone marrow aspirate tube, 3-5 unstained slides, and buccal swab should be shipped to the following address:

MD Anderson Department of Pathology
Tissue Qualification Laboratory
[name]
[name]
[name],
[name]

An email should be sent to the MD Anderson TQL at [contact] prior to sending the specimen alerting the laboratory that the specimen is being shipped.

9.4.1.3. Shipping of Specimen(s)

After tissue processing by the MD Anderson MDL, DNA and cDNA will be shipped according to the laboratory manual for shipping specimens from the MD Anderson TQL to the NCI MoCha laboratory. Nucleic acids shipped to the MoCha laboratory should be labeled as per the Specimen Tracking Instructions (Section 9.1.1.1.).

9.4.1.4. Site(s) Performing Correlative Study

The NCI Molecular Characterization (MoCha) Laboratory.

9.5. Optional biobanking of blood and marrow samples

Optional biobanking will be available for blood and left-over bone marrow aspirate samples collected during the study for future analyses. These samples may be used for further exploratory studies, which include genomic sequencing, based on emerging scientific knowledge to better understand the target disease, the effects of study treatment, and potential mediators of primary and acquired resistance to therapy. Consent will be obtained per the ICF from subjects who wish to participate in optional sample biobanking.

For optional serum banking, approximately 10 mL of blood will be collected in a heparin (green top) tube to bank viably frozen peripheral blood mononuclear cells, and approximately 7 mL of blood will be collected in a red top tube for serum banking. Blood specimens should be labeled as per the Specimen Tracking Instructions (Section 9.1.1.1.) Collection of optional blood sample for biobanking will occur at screening outlined in the Study Calendar (Section 10.).

For study sites outside of MD Anderson, blood samples for biobanking should be kept at room temperature until same-day overnight shipping at ambient temperature to MD Anderson in same shipping container as bone marrow aspirate tubes and unstained slides as described in Section 9.1.1.2.

9.6. Other studies: Minimal Residual Disease Testing

Minimal residual disease (MRD) testing will be assessed as per standard of care per the updated 2016 IMWG response guidelines (Appendix F). In this study, MRD will be assessed using the CLIA-certified clonoSEQ® (Adaptive Biotechnologies) VDJ NGS assay.

In subjects achieving a biochemical complete response (CR) defined as a negative SPEP, UPEP, serum IFE, and urine IFE, a bone marrow biopsy and aspiration will be performed to confirm CR and to assess for MRD using the clonoSEQ® assay. In subjects achieving MRD negativity, a bone marrow biopsy and aspirate may subsequently be performed every 12 months (+/- 30 days) to evaluate for sustained MRD per IMWG response criteria (see Appendix F).

Sample Collection:

Immediately after marrow is aspirated, place 2 mL of bone marrow aspirate into sterile EDTA (lavender top) tube. Mix well by inversion.

Handling of Specimens(s)

Specimens should be stored at ambient room temperature until same day overnight shipping.

Shipping of Specimen(s).

Bone marrow aspirate specimen for in EDTA tube should be shipped at ambient temperature overnight to the following address:

MD Anderson Department of Pathology
Tissue Qualification Laboratory
[name]
[name]
[name],
[name]

Archived DNA from the subject's myeloma cells that was banked from the pretreatment screening bone marrow aspiration as per Section 9.1.1.2. will also be sent concurrently to

Adaptive Biotechnologies and will be used to identify the dominant clonotype(s) and “tracking” sequence for MRD detection using the clonoSEQ® assay.

clonoSEQ® ID gDNA and tracking specimens (bone marrow aspirate samples stored in EDTA tube at -80 degrees Celsius until ready for shipment) will be shipped in batch. Coordinating site (MDACC) will email [contact] the sample type, number of total samples, how many samples for clonality/ID vs tracking/MRD and the contact name, shipping address and phone number to receive a shipper with FedEx return shipping label.

When coordinating site (MDACC) is ready to ship samples, the shipping manifest will be completed and a hard copy to include in the shipper with the samples. Shipping manifest and FedEx tracking number will be emailed to [contact]. Samples should be shipped no later than a Wednesday. For shipping near a holiday, please contact [contact].

9.7. Summary of Bone Marrow Biopsy and Aspirate Studies

Study	Baseline	Post Cycle 1	Complete remission	End of Study
DNA and RNA sequencing for integral, integrative, and exploratory studies.	X	X		X
Pathology review/immuno-Histochemistry*	X	X	X	X
Flow Cytometry*	X	X	X	X
FISH/Cytogenetics*	X			X
ClonoSEQ® VDJ NGS for MRD testing	X		X	X
Biobanking	X	X	X	X

*Testing will be performed at local study site as per standard of care

10. STUDY CALENDAR

10.1. Part A: Dose Escalation

Cycle (a)	Pre-Cycle	Cycle 1			Cycle 2	Cycle 3-12	Cycle 13-18	Cycle 18+	Post-Cycle
Visit Number	1	2	3	4	5	TBD	TBD	TBD	TBD
Visit Description	Screening	Exam and 1 st dose	Exam	Exam	Exam	Exam	Exam	Exam	EOT (b)
Cycle Day(s)	-28 to 0	1	8	15	1	1	1	1	ND
Visit Window (days)			+/-2	+/-2	+/-4	+/-4	+/-4	+/-4	+/-5
KRT-232 (AMG 232)		A			A	A	A	A	
Carfilzomib		B1			B1	B1	B2		
Lenalidomide		C			C	C	C	C	
Dexamethasone		D			D	D	D	D	
Informed Consent	X								
Demographics	X								
Medical History (c)	X								
Adverse events	X	X	X	X	X	X	X	X	X
Prior/concomitant medications	X	X	X	X	X	X	X	X	X
ECOG performance status	X	X	X	X	X	X	X	X	X
Vital signs	X	X	X	X	X	X	X	X	X
Height	X	X							
Physical Exam, including weight (c)	X	X	X	X	X	X	X	X	X
CBC with diff, platelets	X	X (d)	X	X	X (e)	X (e)	X (e)	X	X
Serum chemistries (f)	X	X (d)	X	X	X (g)	X (g)	X (g)	X	X
aPTT, PT, and INR	X								
Hepatitis panel (h)	X								
Urine or serum β-HCG (i)	X	X	X	X	X	X	X	X	X
Myeloma laboratory assessment (j)	X	X			X	X	X	X	X
Bone marrow aspiration and biopsy (k)	X				X (l)				X (l)
TP53 status (NGS)	X								
Blood sample for drug exposure measurement (m)		X				a			
MIC-1 serum sample (n)	X	X							
Buccal mucosal swab	X								
Blood sample for banking (o)	X								
Myeloma bony survey (p)	X								
Echocardiogram	X								
Dispense KRT-232 (AMG 232)		X			X	X	X	X	X
Pill diaries dispensed/reviewed		X	X	X	X	X	X	X	X

A: KRT-232 (AMG 232), dose as assigned, Day 1 through D7

B1: Carfilzomib 20 mg/m² IV on Days 1 and 2 of Cycle 1, escalating to 27 mg/m² IV on Days 8, 9, 15, 16 of Cycle 1 and continuing on Days 1, 2, 8, 9, 15, 16 of Cycles 2 through Cycle 12

B2: Carfilzomib 27 mg/m² IV on Days 1, 2, 15, and 16

C: Lenalidomide 25 mg PO on Days 1-21

D: Dexamethasone 40 mg PO or IV on Days 1, 8, 15, and 22

- a. Each cycle will last 28 days. Cohort safety assessment for DLTs will be performed after Day 28 of Cycle 1.
- b. End-of-Treatment Visit will occur 30 (\pm 5) days after the last administration of KRT-232 (AMG 232). If the subject begins another form of anticancer therapy before the end of the 30 (\pm 5)-day period, every effort will be made to complete all the End-of-Treatment assessments prior to commencing the new therapy. If there is an abnormality in need of monitoring beyond the End-of-Treatment Visit, subjects will be followed until resolution or confirmed stability of the abnormality.
- c. A complete history & physical examination should be performed at screening. Thereafter, only a symptom-directed physical exam is required.
- d. CBC and serum chemistries for Cycle 1/Day 1 pre-dose can be collected within 48 hours before the first dose.
- e. CBC are collected pretreatment (within 48 hours) on Days 8 and 15 during Cycles 2-12 and Day 15 during Cycles 13-18.
- f. Serum chemistries: Albumin, alkaline phosphatase, total bilirubin, bicarbonate, BUN, calcium, chloride, creatinine, glucose, LDH, phosphorus, potassium, total protein, SGOT [AST], SGPT [ALT], sodium, magnesium.
- g. Basic Metabolic Panel (bicarbonate, BUN, calcium, chloride, creatinine, glucose, potassium, sodium) are collected pretreatment (within 48 hours) on Days 8 and 15 during Cycles 2-12 and Day 15 during Cycles 13-18.
- h. Hepatitis panel will include HAV Ab, qualitative HBsAb, HBsAg, HBcAb, and HCV Ab
- i. Two negative pregnancy tests must be obtained prior to initiating therapy in female subjects of childbearing potential during the screening period. The first test should be performed within 10-14 days and the second test within 24 hours prior to initiating therapy and then weekly during the first month, then monthly thereafter in women with regular menstrual cycles or every 2 weeks in women with irregular menstrual cycles as per the lenalidomide Risk Evaluation and Mitigation Strategy (REMS) program.
- j. Myeloma laboratory assessment includes serum free light-chain assay, serum protein electrophoresis (and immunofixation if needed to confirm CR if no M-protein detected on electrophoresis), serum quantitative immunoglobulins (IgG, IgA, IgM), 24-hour urine protein electrophoresis (and immunofixation if needed to confirm CR if no M-protein detected on electrophoresis), and β 2-microglobulin. Initial pretreatment assessment can be collected within 1 week of first dose.
- k. Initial pretreatment/screening bone assessment requires bilateral biopsy and aspirates. Can occur within 4 weeks of first dose date. Bone marrow analysis should include morphologic review, quantification of percentage of plasma cells, flow cytometry, and myeloma fluorescence *in situ* hybridization (FISH) panel (performed locally) as per standard of care.
- l. Optional bone marrow biopsy and aspiration for Cycle 2/Day 1 may be performed anytime from Cycle 1/Day 24 to Cycle 2/Day 5. Mandatory bone marrow biopsy and aspiration at EOT would be performed within 30 days following the last study treatment, preferably prior to initiating new therapy. In patients achieving a biochemical CR (negative SPEP/UPEP and urine/serum IFE), an additional bone marrow should be performed to confirm a CR with MRD testing using the clonoSEQ® NGS assay (Adaptive Biotechnologies) with minimum sensitivity to 10^{-5} nucleated cells. In patients achieving MRD negativity, a bone marrow biopsy and aspirate may subsequently be performed every 12 months (+/- 30 days) to evaluate for sustained MRD.
- m. Blood samples for drug exposure measurement will be collected Cycle 1/Day 1 pre-dose and post-dose at 1 hr, 3 hr, 5 hr, 8 hr, and 24 hr (C1D2).

- n. Blood samples for MIC-1 testing will be collected at screening, Cycle 1/Day 1 pre-dose, and post-dose at 24 hr (C1D2)
- o. Blood samples for optional biobanking will be collected at screening. Approximately 10 mL of blood will be collected in a heparin (green top) tube and approximately 7 mL of blood will be collected in a red top tube.
- p. One additional bony survey may be performed solely to confirm a CR, if this is indicated by serum and urine immunofixation assays.

ECOG = Eastern Cooperative Oncology Group; EOT = End of Treatment; MIC-1 = macrophage inhibitory cytokine-1; TBD = to be determined.

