5.6. Definition of Dose-Limiting Toxicity

A DLT is defined as any treatment emergent adverse event (TEAE) during the first treatment cycle that does not have a clear alternative cause (e.g., disease under study, concomitant therapy) based on the following criteria using NCI-CTCAE v5.0:

- Hematological toxicity
 - Grade 3 or 4 neutropenia with fever $\geq 38^0$ C lasting > 48 hours
 - Grade 4 neutropenia lasting > 7 days
 - Grade 3 or 4 thrombocytopenia associated with $>$ grade 1 bleeding. Grade 4 thrombocytopenia that persists for > 14 days, despite holding treatment
 - Grade 4 anemia, unexplained by underlying disease
 - Any other grade 4 hematologic toxicity that does not resolve to subject's pre-treatment baseline level within 72 hours
- Non-hematological toxicity
 - Grade ≥ 3 nausea, vomiting or diarrhea lasting longer than 72 hours despite optimal medical support
 - Grade ≥ 3 non-hematological toxicity (excluding increased serum creatinine, or electrolyte abnormalities that are not clinically significant and require no treatment)
 - Any grade 3 electrolyte abnormalities that do not resolve to grade ≤ 2 within 72 hours
 - Grade 3 fatigue persisting > 7 days
 - Grade ≥ 3 acute kidney injury (creatinine $> 3 \times$ baseline or > 4.0 mg/dL) lasting > 72 hours
 - Any other grade 3 or 4 non-hematologic toxicities not predefined above will be considered a DLT.
 - A delay of ≥ 14 days in commencing Cycle 2 Day 1 due to lack of adequate

recovery of KRT-232 (AMG 232) +KRD-related toxicities will be considered a DLT.

Subjects who receive < 75% of the planned study drug doses during the first cycle of (i.e. $\leq 5/7$ daily doses of KRT-232 (AMG 232) will be considered non-evaluable for purposes of determining the MTD (unless due to a DLT) and will be replaced. Subjects who experience a DLT during the DLT-evaluable period will be considered evaluable for the purposes of determining the MTD as per Section 13.1.4

Management and dose modifications associated with the above adverse events are outlined in Section 6.

Dose escalation will proceed within each cohort according to the following scheme. Dose-limiting toxicity (DLT) is defined above.

Number of Subjects with DLT at a Given Dose Level	Escalation Decision Rule
0 out of 3	Enter 3 subjects at the next dose level.

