13.1.4. Dose-Limiting Toxicity Evaluable Set

The DLT-evaluable set will include all subjects enrolled in the Dose Escalation part who had a DLT within the first 4 weeks (28 days) on study, or without DLT but received at least 75% of scheduled KRT-232 (AMG 232) doses during the first 3 weeks (21 days). Subjects who complete C1 but are removed from study due to a *TP53* mutation and/or deletion are still eligible to be included in the DLT-evaluable set.

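### No blood count or chemistry is required between Cycle 1 Day 15 and Cycle 2 Day 1, so some duration-defined DLTs can begin and resolve unseen

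*Combined protocol and SAP*

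**What the plan says.** Section 13.1.4 counts a subject as having an event if they "had a DLT within the first 4 weeks (28 days) on study". The calendar notes add: "Cohort safety assessment for DLTs will be performed after Day 28 of Cycle 1".

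Several criteria in Section 5.6 depend on how long a laboratory abnormality lasts. One is "Grade 4 neutropenia lasting > 7 days". Another is "Grade 4 thrombocytopenia that persists for > 14 days, despite holding treatment". Any other grade 4 hematologic toxicity counts if it has not returned to baseline within 72 hours, and a grade 3 electrolyte abnormality counts if it has not improved to grade 2 or better within 72 hours.

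The Part A and Part B calendars (10.1, 10.2) carry the same sampling marks: the row "CBC with diff, platelets" and the chemistry row are marked on Cycle 1 Days 1, 8 and 15, then Cycle 2 Day 1. The footnotes add nothing on Days 16 to 28:

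- Footnote d is about the baseline sample only: "CBC and serum chemistries for Cycle 1/Day 1 pre-dose can be collected within 48 hours before the first dose".
- Footnote e starts in Cycle 2: "CBC are collected pretreatment (within 48 hours) on Days 8 and 15 during Cycles 2-12 and Day 15 during Cycles 13-18".
- Footnote g does the same for the basic metabolic panel.

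**The concern.** The cycle that decides escalation is sampled no more often than Cycles 2 to 12, and its second half has no required laboratory sample. That half is not a rest period: carfilzomib is given on Days 15 and 16, and lenalidomide continues to Day 21. Section 2.3.2 names neutropenia and thrombocytopenia among the main KRT-232 toxicities. The adverse reaction table in Section 7.1 shows grade 3 or higher neutropenia in 27% of subjects on KRd alone during Cycles 1 to 12.

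A subject with adequate counts on Day 15, grade 4 neutropenia from Day 17 to Day 26, and recovery by Day 29 meets the Section 5.6 definition but would be scored as having no DLT. Missed events can only lower the observed DLT count, so the error runs toward escalation.

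**Working it through.** **Inputs.** CBC days 1, 8, 15 and 29 (Cycle 2 Day 1 of a 28-day cycle), with windows of ±2 days for Day 15 and ±4 days for Cycle 2 Day 1 (10.1, 10.2). Duration thresholds of more than 7 days, more than 14 days and more than 72 hours (5.6). A DLT rate below 33% is considered acceptable (2.6). Escalation follows 0 of 3, or 1 of 3 and then 0 of 3 (5.4, 5.6).

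**Gap.** Days 1 to 8 and 8 to 15 are 7 days each. Day 15 to Day 29 is 14 days. Within windows the minimum is 25 − 17 = 8 and the maximum is 33 − 13 = 20.

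**Chance that an episode starting in the gap meets no required sample.** Assume onset uniform over a gap of G days and an episode of D days. The chance is max(0, (G − D)/G). An 8-day episode is the shortest whole-day neutropenia over 7 days; a 4-day episode stands for the 72-hour criteria.

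| Episode | G = 14 (nominal) | G = 8 (shortest) | G = 20 (longest) | Day 22 added (two 7-day gaps) |
|---|---|---|---|---|
| 4 days | 10/14 = 71% | 4/8 = 50% | 16/20 = 80% | 3/7 = 43% |
| 8 days | 6/14 = 43% | 0% | 12/20 = 60% | 0% |
| 15 days | 0% | 0% | 5/20 = 25% | 0% |

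In whole days, an 8-day episode starting on any of Days 16 to 21 is over before Day 29. A platelet event of more than 14 days fits only if windows stretch the gap beyond 14 days.

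**Effect on escalation.** With true DLT risk p and a share g of DLTs unseen, the observed risk is q = p(1 − g), and P(escalate) = (1 − q)³ + 3q(1 − q)²(1 − q)³. At p = 0.33:

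- g = 0: q = 0.330, P = 43%
- g = 5%: q = 0.3135, P = 47%
- g = 10%: q = 0.297, P = 50%
- g = 20%: q = 0.264, P = 57%

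The documents give no value for g, so these are illustrations. For scale, with onset uniform over all 28 days, 6/28 = 21% of 8-day episodes and 10/28 = 36% of 4-day episodes would fall wholly inside the gap. A g of 20% would therefore need nearly every DLT to be one of these short laboratory events.

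**Part B.** The Section 5.7 probabilities reproduce: 22.1%, 68.7% and 96.7% for 3 or more DLTs among 11 subjects; 7.9%, 55% and 96.2% for 5 or more among 16. They assume that every DLT is seen. At a true rate of 30%, the 55% falls to 44% if 10% are missed and to 33% if 20% are missed.

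**The case against.** The plan has other ways of finding cytopenia. Grade 3 or 4 neutropenia on Day 15, or platelets below a Section 6.4 threshold, starts weekly CBCs, which would give a count near Day 22. Section 6.1 requires neutrophil and platelet recovery before Cycle 2. Fever or bleeding would prompt an unscheduled count, and nothing forbids one. Some KRT-232 management text in Sections 6.3 and 6.4 is redacted, so triggered monitoring cannot be judged in full.

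This narrows the point without removing it. The weekly CBC starts only after a low value has been seen. The Cycle 2 check finds only what is still present, and one abnormal value there does not date the onset. Day 22 dexamethasone may be taken orally at home and recorded in the diary, so it does not imply a visit. Unscheduled counts are optional, so ascertainment would vary by site and symptoms.

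A reader might infer more than the documents support:

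- *That the schedule hides the overlapping thrombocytopenia named in Section 2.6.* At nominal visit days it cannot hide the 14-day platelet criterion, whose wording about holding treatment presumes that the count is already known. The other platelet criterion requires bleeding.
- *That a large share of all DLTs is lost.* Section 5.6 also counts many symptomatic non-hematologic events and a delayed Cycle 2, and Section 5.4 counts dose reductions in Cycle 1. All of these dilute the missed share.
- *That Cycle 1 DLT is itself the primary endpoint.* Section 13.2 names safety, tolerability and MTD/RP2D. The DLT-evaluable set covers dose escalation only, and in Part B DLTs trigger a discussion (5.7).

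**Conclusion.** The point holds as a gap in required ascertainment; it does not show that events will be missed. It applies to subjects whose Day 15 counts do not trigger weekly CBCs, and to grade 4 neutropenia of more than 7 days and the 72-hour hematologic and electrolyte criteria. The 14-day platelet criterion is affected only through stretched visit windows.

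The 43% and 71% rest on uniform onset within the nominal gap and apply to episodes of the shortest qualifying length. Longer neutropenias are missed less often: (14 − 10)/14 = 29% at 10 days. Onset clustered late in the cycle would change these figures, and no document gives an onset distribution. The direction, toward escalation, does not depend on these assumptions; the size of the shift does. It would be wrong to read the result as cytopenias going unmonitored. This is a worthwhile, inexpensive improvement.

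**What to change.** Add a CBC with differential and a basic metabolic panel at Cycle 1 Day 22 (±2 days, local draw allowed) to the calendars in 10.1 and 10.2. This continues the plan's own weekly spacing from Days 1 to 15. Even at the window extremes, the longest interval without a sample after Day 15 falls from 20 days to 33 − 20 = 13.

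The cost is one routine draw per subject, in Cycle 1 only. Women of childbearing potential already have weekly pregnancy tests in the first month (footnote i), so some subjects need a contact near Day 22 anyway.

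The limits should be stated. The 72-hour criteria remain only partly observed (43% of 4-day events still missed at nominal days). The basic metabolic panel in footnote g omits magnesium and phosphorus. The 0% for 8-day events holds at nominal visit days.

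A rule that treats an abnormal value as persisting until shown otherwise is not recommended. It would turn a single unrepeated value into a DLT, which is a debatable rewrite of the definition, and it would do nothing for events that no sample sees.

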5.4. KRT-232 (AMG 232) + Carfilzomib, Lenalidomide, and Dexamethasone Treatment Plan

Dose Regimen

KRT-232 (AMG 232) + carfilzomib, lenalidomide, and dexamethasone will be administered per the following schedule:

Cycles 1-12 (28 day cycle)

- KRT-232 (AMG 232) once daily by mouth 7 out of 28 days
- Carfilzomib 20 mg/m² IV on Days 1 and 2 of Cycle 1, escalating to 27 mg/m² IV on Days 8, 9, 15, 16 of Cycle 1 and continuing on Days 1, 2, 8, 9, 15, 16 of Cycles 2 through Cycle 12
- Lenalidomide 25 mg PO on Days 1-21
- Dexamethasone 40 mg PO or IV on Days 1, 8, 15, and 22

Cycles 13-18 (28 days each)

- KRT-232 (AMG 232) once daily by mouth 7 out of 28 days
- Carfilzomib 27 mg/m² IV on Days 1, 2, 15, and 16
- Lenalidomide 25 mg PO on Days 1-21
- Dexamethasone 40 mg PO or IV on Days 1, 8, 15, and 22

Cycles 19+ (28 days each)

- KRT-232 (AMG 232) once daily by mouth 7 out of 28 days
- Lenalidomide 25 mg PO on Days 1-21
- Dexamethasone 40 mg PO or IV on Days 1, 8, 15, and 22

Part A (Dose-escalation scheme)

The MTD is defined as the highest dose at which six subjects have been treated and less than two subjects experienced DLT within the first cycle of treatment in Phase I of the trial. To determine the MTD, escalation for KRT-232 (AMG 232) will be conducted following the “3+3” design with de-escalation. A cohort of three subjects will be treated at the starting dose level and observed until the end of the first cycle (subjects non-evaluable for DLT will be replaced). The dose level will be escalated with each new cohort until at least one out of three subjects of a cohort experiences DLT. If one subject experiences a DLT, then three additional subjects will be treated at the same dose level; if none of the three additional subjects experiences a DLT, then the dose escalation will be continued by treating the next cohort of three subjects at the next higher dose level. If at least two out of up to six subjects at a dose level experience a DLT, the MTD will be considered to have been exceeded, and up to 3 more subjects will be treated at the next lower dose if there are less than 6 subjects already treated at that dose. The dose steps for escalation are displayed below:

Dose Escalation Schedule	
Dose Level	Dose of KRT-232 (AMG 232)*
- 1	30 mg/day PO x 7 days out of 28 day cycle
+ 1	60 mg/day PO x 7 days out of 28 day cycle
+ 2	90 mg/day PO x 7 days out of 28 day cycle
+ 3	120 mg/day PO x 7 days out of 28 day cycle

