≥ 2	Dose escalation will be stopped. This dose level will be declared the maximally administered dose (highest dose administered). Three (3) additional subjects will be entered at the next lowest dose level if only 3 subjects were treated previously at that dose.
1 out of 3	Enter at least 3 more subjects at this dose level. If 0 of these 3 subjects experience DLT, proceed to the next dose level. If 1 or more of this group suffer DLT, then dose escalation is stopped, and this dose is declared the maximally administered dose. Three (3) additional subjects will be entered at the next lowest dose level if only 3 subjects were treated previously at that dose.
≤ 1 out of 6 at highest dose level below the maximally administered dose	This is generally the recommended phase 2 dose. At least 6 subjects must be entered at the recommended phase 2 dose.

5.7. Dose Expansion Cohorts:

Once the RP2D is reached, a goal of 10 additional subjects will be treated at this dose. For the expansion cohort, subjects will continue to be monitored for occurrence of DLT. If 2 of the first 5 subjects or if ≥ 4 of 10 subjects experience DLT, the Principal Investigator will discuss with all study investigators and with CTEP whether further addition of subjects is needed to re-assess the RP2D. When the first 5 additional patients are enrolled in the expansion phase, with a total of 11 patients including the 6 patients who had been already treated at the RP2D, the probabilities of observing 3 or more patients with DLT are 22.1%, 68.7% and 96.7% if the true toxicity rate are 15%, 30%, and 50%. When all 10 additional patients are enrolled in the expansion phase, with a

total of 16 patients including the 6 patients who had been already treated at the RP2D, the probabilities of observing 5 or more patients with DLT are 7.9%, 55%, and 96.2% if the true toxicity rate are 15%, 30%, and 50%. Monitoring of all safety and toxicity data is done by the Principal Investigator and the Corresponding Organization on a real-time basis as data are entered into Medidata Rave using the Web Reporting Module. All participating sites are expected to notify the Principal Investigator when a DLT has occurred.

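### Part A cohort decisions may be taken once Day 28 has passed, before some Section 5.6 DLTs can be known, and no written rule makes the decision wait

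*Combined protocol and SAP*

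**What the plan says.** **Timing of the decision.** Protocol Section 5.4 has each cohort of three "observed until the end of the first cycle". Footnote a of Section 10.1 sets the cycle at 28 days and adds: "Cohort safety assessment for DLTs will be performed after Day 28 of Cycle 1". The decision table in Section 5.6 then opens the next level when 0 of 3 subjects have a DLT.

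**Criteria that need time.** Section 5.6 includes "Grade 4 thrombocytopenia that persists for > 14 days, despite holding treatment" and "Grade 4 neutropenia lasting > 7 days". It also counts as a DLT a delay of 14 or more "days in commencing Cycle 2 Day 1 due to lack of adequate" recovery from treatment-related toxicity. Section 6.1 repeats that such a delay is a DLT and points back to Section 5.6.

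**Who is counted.** Section 13.1.4 builds the DLT-evaluable set from Part A subjects "who had a DLT within the first 4 weeks (28 days) on study", plus subjects without a DLT who received at least 75% of scheduled KRT-232 doses in the first 21 days.

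**Oversight.** Section 12.1 requires Protocol Principal Investigator sign-off for each escalation decision, and calls at least monthly with the study investigators and the CTEP Medical Officer.

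**The concern.** The MTD and RP2D are a primary objective of Part A, and they rest on counts of 0, 1 or 2 DLTs in three to six subjects. One DLT that is not yet countable changes the decision.

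The affected criteria are relevant to this regimen. Section 2.6 names thrombocytopenia as an overlapping toxicity to be watched. Carfilzomib is given on Days 15 and 16 and lenalidomide runs to Day 21, so cytopenia late in Cycle 1 is plausible. The calendar schedules blood counts in Cycle 1 on Days 1, 8 and 15, and then at Cycle 2 Day 1 (plus or minus 4 days). A late cytopenia may therefore first be seen at about the earliest decision date.

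Two things could follow. Three subjects could start a higher dose while a DLT at the lower dose is unresolved. Separately, an event that meets its criterion after Day 28 could be lost from the final count because of the window in Section 13.1.4.

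**Working it through.** **The plan's own figures.** The plan gives no operating characteristics for Part A escalation. Its only DLT probabilities are those for Part B in Section 5.7, and they reproduce as binomial tails. P(at least 3 of 11) is 0.221, 0.687 and 0.967, and P(at least 5 of 16) is 0.079, 0.550 and 0.962, at true rates of 15%, 30% and 50%. These values treat all 11 or 16 subjects as fully followed for DLT.

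**Day arithmetic for Part A.** The first day on which a duration criterion is exceeded is onset + 14 (more than 14 days) or onset + 7 (more than 7 days) if the onset day is counted as a day. It is one day later if elapsed days are counted.

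| Criterion (Section 5.6) | Onset | First day it can be met |
|---|---|---|
| Grade 4 thrombocytopenia > 14 days | Day 15 | 29 or 30 |
| Same | Day 28 | 42 or 43 |
| Grade 4 neutropenia > 7 days | Day 22 | 29 or 30 |
| Same | Day 28 | 35 or 36 |
| Cycle 2 Day 1 delayed by >= 14 days | any | 29 + 14 = 43 |

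The last row needs no assumption about onset: no subject can meet that criterion by Day 28.

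**Sections side by side.** Sections 5.6 and 6.1 call the Cycle 2 delay a DLT. Section 13.1.4 admits only DLTs within 28 days. If its phrase about subjects without a DLT refers to that window, a subject whose delay qualifies on Day 43 and who took the required doses counts as DLT-free. If the phrase means no DLT at any time, the subject fits neither part of the definition and leaves the set. Either way the event is lost. Section 6.1 delays only the affected subject's own next cycle. No section holds the cohort decision.

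**Illustrative size.** Inputs:
- True DLT rate p = 0.40, q = 0.60. This is above the 33% bound that Section 2.6 treats as acceptable.
- Accrual of 1.5 or 2.5 subjects per month; both figures stand in Section 13.3.
- Share f of DLTs not determinable at Day 28. This is an assumption, taken as 10%, 25% and 50%, with those DLTs becoming known evenly over Days 28 to 42.
- A 30.4-day month with even spacing, and a decision when the third subject reaches Day 28.

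The three subjects are then at Days 69, 48 and 28 (1.5 per month) or Days 52, 40 and 28 (2.5 per month). The chance that a subject has a DLT visible at the decision is v = p(1 - f x r), where r is the part of Days 28 to 42 still to run. At 1.5 per month r = 0, 0, 1. At 2.5 per month r = 0, 0.13, 1.

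Let A = (1 - v1)(1 - v2)(1 - v3), the chance that no DLT is visible. Let B = (v1 + v2 + v3) x q^2, the chance of one visible DLT and no other, visible or pending. Pending DLTs in the first three subjects are carried forward, because they are known by the six-subject decision. Then P(escalate) = A + B x A.

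- f = 0: A = 0.216, B = 0.432, P = 0.309.
- 1.5 per month, f = 25%: A = 0.6 x 0.6 x 0.7 = 0.252; B = (0.4 + 0.4 + 0.3) x 0.36 = 0.396; P = 0.352.

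| f | 1.5 per month | 2.5 per month |
|---|---|---|
| 0 | 0.309 | 0.309 |
| 10% | 0.327 | 0.329 |
| 25% | 0.352 | 0.358 |
| 50% | 0.392 | 0.406 |

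**The case against.** **Day 28 is a minimum.** The footnote does not oblige anyone to decide with an event open, and Section 12.1 provides Principal Investigator sign-off and regular calls. A reader might infer that the protocol forces premature escalation. It does not. What stands is that the protocol permits it and has no rule for pending events.

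**A delayed cycle might be read as not yet ended.** On that reading the Section 5.4 observation period would stretch until Cycle 2 starts. Footnote a fixes each cycle at 28 days and Section 13.1.4 gives the window as 28 days, so the text does not support this.

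**Late thrombocytopenia can count by other routes.** Grade 3 or 4 thrombocytopenia with bleeding above Grade 1 is a DLT without waiting, and so is a required Cycle 1 dose reduction (Sections 5.4, 5.6 and 6). This is correct. The Day 15 cut-off applies only to the persistence criterion, and most criteria in Section 5.6 need 72 hours or less, or no duration. The share of onset days affected is therefore not the share of DLTs affected.

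**Part B.** A reader might take "When the first 5 additional patients are enrolled in the expansion phase, with a total of 11 patients" in Section 5.7 to mean that safety looks occur at enrolment, before Cycle 1 is complete. The trigger itself depends on subjects who experience a DLT, with real-time monitoring, and the Part B calendar repeats the after-Day-28 footnote. The enrolment wording belongs only to the probability statements, and Part B has no escalation. The concern does not extend there.

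**Size.** Larger effects result if all three subjects are assumed to enrol together. That departs from the stated accrual rates and is not used here.

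**Conclusion.** The point holds for Part A as a missing hold rule together with a contradiction between sections. The day arithmetic and the conflict between Section 13.1.4 and Sections 5.6 and 6.1 rest on the text alone. The numerical effect is illustrative: at a true DLT rate of 40%, the chance of escalating rises by about 2 percentage points if 10% of DLTs are pending, 4 to 5 points if 25% are, and 8 to 10 points if 50% are. The pending share and its even spread over Days 28 to 42 are assumptions, and since few of the criteria are long-duration ones the upper end should not be taken as expected. The documents do not show that escalation will occur with a DLT unresolved, only that nothing prevents it. This should be corrected because it bears on the primary endpoint and is cheap to repair.

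**What to change.** Reconcile Sections 5.4, 5.6, 6.1, 10.1 (footnote a) and 13.1.4, and the matching synopsis text, on two matters:

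1. State that the cohort decision is made only when every subject's DLT status under the existing Section 5.6 criteria is determined. Any event ongoing at Day 28 under a duration criterion must have resolved or passed its threshold, and any pending Cycle 2 Day 1 delay must be settled.
2. State in Section 13.1.4 that an event beginning in Cycle 1 that meets its criterion later, or a qualifying Cycle 2 Day 1 delay, counts in the DLT-evaluable set for that cohort.

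No DLT threshold or dose needs to change for this. In Section 5.7, at most add that the stated probabilities assume all 11 or 16 subjects have completed DLT follow-up.

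The cost is protocol wording, no extra subjects, and a wait of about two weeks (Day 28 to about Day 43) only when an event or a delay is pending.
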